### **Assessment of complications and mortality**

Postoperative pulmonary complications were identified and categorized based on European Perioperative Clinical Outcome (EPCO) definitions from the ESA-ESICM joint taskforce on perioperative outcome measures. These include respiratory infection, respiratory failure, pleural effusion, atelectasis, pneumothorax, bronchospasm, aspiration pneumonitis.

Major adverse cardiac and cerebrovascular events (MACCE) was a composite outcome of non-fatal cardiac arrest, acute myocardial infarction, congestive heart failure, new cardiac arrhythmia, angina, ischemic stroke.

Sepsis was defined according Sepsis-3 definition.

We performed separate analyses of complications apparently related to surgical technique (for instance, anastomotic leakage, fistula, abscess, hemorrhage) and medical complications, i.e. pulmonary, cardiovascular (acute myocardial infarction, atrial fibrillation, cardiogenic shock) and septic.

All complications were evaluated 30 days after surgery.

Mortality in hospital after resection of esophageal cancer was defined as any death during the admission when the operation was performed. This was more reliably quantified than 30-day mortality.

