## **SECONDARY ENDPOINTS**

- Distinction between transient and persistent AKI
- Occurrence of recovery or progression at 7 days, 30 days and 3 months
- Association between AKI and pulmonary complications, major adverse cardiovascular events, anastomotic or septic complications, or death.
- Identify risk factors associated with AKI occurrence.

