## **DATA COLLECTION**

A team properly instructed will collect patient's data, which will be filled in a CRF (Case Report Form). An electronic copy of CRF will be retained in Microsoft Excel format.

All collected data will be identified and stored in such a way as to protect patient confidentiality. The staff involved in the collection and management of data will not use or disseminate such information for purposes other than those provided for the realization of the study.

All data will be collected and processed in a completely anonymous way, in compliance with the guarantee terms of privacy and as approved by Comitato Etico per la Sperimentazione Clinica della Provincia di Padova.

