**Outcomes:**

need for RRT: \_\_\_\_\_days

MACCE within 30 days:  AMI

congestive heart failure

non-fatal cardiac arrest

new cardiac arrhythmia

angina

stroke

pulmonary complications within 30 days:  respiratory infection at \_\_\_\_day (i.e. patients has received antibiotics for a suspected respiratory infection + one of the following: new or changed sputum, new or changed opacities, fever, wbc >12000)

respiratory failure at \_\_\_\_day (PaO2 < 60 mmHg at room air, a P/F < 300 mmHg or SpO2 <90% requiring oxygen therapy)

pleural effusion at \_\_\_\_day

atelectasis at \_\_\_\_day

pneumothorax at \_\_\_\_day

bronchospasm at \_\_\_\_day (bronchodilators treatment for new expiratory wheezing)

aspiration pneumonitis at \_\_\_\_day

length of CMV \_\_\_\_h

need for NIV in \_\_\_\_\_h

surgical complications within 30 days:  fistula       hemorrhage       abscess

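### The planned analysis of infarction, atrial fibrillation and cardiogenic shock cannot be run as written: the CRF has a dedicated postoperative field for only one of the three

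*Combined protocol and SAP*

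**What the plan says.** All references are to the combined protocol and SAP.

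- **Secondary Endpoints** asks for an "Association between AKI and pulmonary complications, major adverse cardiovascular events, anastomotic or septic complications, or death".
- **Assessment of complications and mortality** defines MACCE as a "composite outcome of non-fatal cardiac arrest, acute myocardial infarction, congestive heart failure, new cardiac arrhythmia, angina, ischemic stroke". Further on, the same section separates complications of surgical technique from medical ones and gives the cardiovascular part of the medical group as "cardiovascular (acute myocardial infarction, atrial fibrillation, cardiogenic shock". It adds: "All complications were evaluated 30 days after surgery".
- **Data Collection** makes the form the source of the analysis data: patients' data are to be collected by a trained team, "which will be filled in a CRF (Case Report Form").
- **Case Report Form, Outcomes** has a 30-day MACCE block with six items: infarction, congestive heart failure, non-fatal cardiac arrest, "new cardiac arrhythmia", angina and stroke. No arrhythmia type or stroke type is asked for, and shock is not listed.

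**The concern.** The plan states an analysis for which its own data form does not collect the components. If nothing changes, the analysts will either drop the three-component group without saying so, or replace it with something they can build, such as infarction plus any new arrhythmia. That substitute would be a different outcome, and it would not have been planned.

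The stroke mismatch is of the same kind. The composite that can be assembled from the form is not quite the composite that is defined.

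The Introduction gives the atrial fibrillation component some interest, because the most recent study it cites found acute kidney injury to be associated with atrial fibrillation. With atrial fibrillation merged into all new arrhythmias, this study could not speak to that result.

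**Working it through.** No sample size, power or event count is involved, so the check is a component-by-component comparison of the two lists with the form.

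**Second list (medical complications, cardiovascular)**

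| Component | Dedicated postoperative field? | Nearest field on the form |
|---|---|---|
| Infarction | Yes | Outcomes, MACCE block |
| Atrial fibrillation | No | Untyped new-arrhythmia box in Outcomes |
| Cardiogenic shock | No | None |

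Count: 1 of 3 components has its own field, and 3 − 1 = 2 do not.

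**Can other parts of the form fill the two gaps?**

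1. *Cardiovascular Tests* has an item for atrial fibrillation on the EKG. It stands between the preoperative laboratory tests and the intraoperative data, so it is a baseline finding. It cannot show the type of an arrhythmia that arises after surgery.
2. *Intraop Data* has an item for arrhythmia during the operation. It too is untyped.
3. The new-arrhythmia box in *Outcomes* would capture new postoperative atrial fibrillation, but together with every other new arrhythmia. A tick does not identify atrial fibrillation.
4. The *Postop* table has rows for vasopressors, inotropes, troponin and BNP. The plan gives no rule that turns these into cardiogenic shock, and the two drug classes may be given for other reasons.
5. The congestive heart failure box in *Outcomes* does not say whether shock was present.
6. The grading of complications has a grade for single-organ dysfunction, but it does not name the organ.

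None of the six yields either missing component.

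**MACCE composite**

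| Component as defined | On the form |
|---|---|
| Non-fatal cardiac arrest | Same |
| Infarction | Same |
| Congestive heart failure | Same |
| New arrhythmia | Same |
| Angina | Same |
| Ischemic stroke | Stroke, type not recorded |

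Count: all 6 components have a field, 5 of them in matching terms and 1 broader than its definition. A patient whose only event is a non-ischemic stroke counts on the form but not under the definition. If no such patient exists, the two versions coincide. The documents give no rates from which to judge how often this would happen.

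**Overlap of the two lists.** Infarction is the only component named in both. Atrial fibrillation is at most a part of "new cardiac arrhythmia", and cardiogenic shock is not a MACCE component. The second analysis therefore cannot be recovered from the MACCE block.

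**The case against.** The strongest reply is that the main cardiovascular outcome is in good order. The endpoint speaks of "major adverse cardiovascular events", the assessment section defines a composite under nearly the same name, and the form collects that composite over 30 days. The second list is a parenthesis in a sentence whose purpose is to separate surgical from medical complications. Neither Aim of the Study nor Secondary Endpoints sets an objective specific to atrial fibrillation. All of this stands, and it is why the point is minor. It does not rescue the second analysis, which the plan says is performed and for which two of three components are not separately recorded.

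A reader might infer more than the documents support in three ways.

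- *That the form does not record atrial fibrillation at all.* It does, before surgery, and new postoperative cases would fall under the arrhythmia box. What is missing is a postoperative field that identifies them.
- *That the endpoint has two rival definitions, one of which could be chosen after the results are seen.* The natural reading ties the endpoint to MACCE. The second list also cannot be derived from the planned data, so it is not available to be chosen. What remains is that the endpoint does not name the composite outright, which one sentence would settle.
- *That arrhythmias would dominate the composite, so that its association with kidney injury would be an arrhythmia result.* The documents give no component rates, so nothing supports this either way.

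**Conclusion.** The point holds in a limited form. The separate cardiovascular analysis of medical complications cannot be run as written, because only 1 of its 3 components has a dedicated postoperative field. The MACCE composite can be assembled, with one of its 6 components collected more broadly than defined.

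This rests on two readings: that the form as printed is the full data source, as Data Collection implies, and that the atrial fibrillation item among the cardiovascular tests is preoperative, as its position indicates. The effect on any estimate cannot be sized from the documents. The primary endpoint, the incidence of acute kidney injury within 48 hours, is unaffected. Severity is minor.

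**What to change.** 1. State in Secondary Endpoints, or in the assessment section, that the MACCE composite is the outcome for the cardiovascular association.
2. Then do one of two things. Either delete the second cardiovascular list, or keep it and add two items to the Outcomes part of the form: postoperative atrial fibrillation, as a subtype of new arrhythmia, and cardiogenic shock. The shock item needs a stated definition, or abstractors will apply their own.
3. Make the stroke component identical in the definition and on the form, whether ischemic only or any type.

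Deleting the list and aligning stroke is a text change. Keeping the list costs two extra fields from the same medical records, on the assumption that those records document the events. It also costs re-review of any charts already abstracted, for example in the 100-patient pilot described under Sample Size.

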## **ETHIC AND SCIENTIFIC DISSEMINATION POLICY**

### **Patient Information/Informed Consent**

As a retrospective analysis, we would base normative n. 9/2014 (“in merito al trattamento dei dati personali effettuato per scopi di ricerca scientifica dell’11 dicembre 2014”).

After completion of the study, the data will be reported at scientific meetings and/or submitted and published in a scientific journal, regardless of the outcome. In these cases, a publication committee will be responsible for these activities and will work with the investigators to determine how the manuscript is written and edited, the number and order of authors, the publication to which it will be submitted, and other related issues.

### **BUDGET OF THE STUDY**

The present study is NO PROFIT.

# CASE REPORT FORM

## Retrospective study on AKI incidence after esophageal cancer surgery

PATIENT ID

### Inclusion criteria:

- elective esophageal cancer patients

### Exclusion criteria:

- Age < 18 years.
- ongoing KRT or ESRD.
- Missing data for AKI criteria (serum creatinine and urine output).
- Second surgery.

### PREOPERATIVE EVALUATION:

Gender  M  F  
Age \_\_\_\_\_ Birthday \_\_\_\_\_  
Weight \_\_\_\_\_ kg Height \_\_\_\_\_ m  
Surgery date \_\_\_\_\_

### COMORBIDITIES:

- COPD Gold class \_\_\_\_
- Interstitial Lung Disease
- pulmonary hypertension
- asthma
- active smokers
- dyspnea
- stroke/TIA
- coronary artery disease
- DM
- hypertension with medication
- active solid organ neoplasm
- hematologic neoplasm
- disseminated cancer
- alcohol use disorder
- dementia
- congestive heart failure in 30 days prior to surgery
- dialysis
- ascites within 30 days prior to surgery
- systemic sepsis within 48 hours prior to surgery
- ventilator dependent

ASA class \_\_\_\_\_

Functional status: Karnofsky \_\_\_\_\_ ECOG \_\_\_\_\_

Weight loss within the last 3 months \_\_\_\_\_

**PREOPERATIVE MEDICATION:**

- Statins
- ACE-inhibitors
- Sartans
- beta-blockers
- PPI
- steroid use in chronic
- NSAIDs
- insulin
- CT
- RT

\_\_\_\_\_

**PREOPERATIVE LABORATORY TESTS**

Hb \_\_\_\_\_ MCV \_\_\_\_\_ Alb \_\_\_\_\_  
sCr \_\_\_\_\_ eGFR \_\_\_\_\_ urea \_\_\_\_\_  
BNP \_\_\_\_\_ Trop \_\_\_\_\_

**CARDIOVASCULAR TESTS**

- AF at EKG
- FE <45%
- carotid stenosis

**RESPIRATORY TESTS**

FEV1 \_\_\_\_\_ FVC \_\_\_\_\_ DLCO \_\_\_\_\_

**INTRAOP DATA**

Type of surgery:  thoracoscopy  thoracotomy  vls  lpt  cervico

Type of anesthesia:

inhaled  TIVA  epidural+inhaled  epidural+TIVA  
 Lidocaine \_\_\_\_mg  Magnesium\_\_\_\_\_mg  Dexamethasone \_\_\_\_\_mg  
 Ranitidine\_\_\_\_\_mg  PPI \_\_\_\_\_mg

NMB:  rocuronium  cisatracurium

NMB reversal:  neostigmine  sugammadex

Duration of anesthesia: \_\_\_\_\_ h

Type of ventilation:  OLV  TLV max FiO2\_\_\_\_\_ min SpO2\_\_\_\_\_

Hemodynamics:

IABP min SBP\_\_\_\_\_mmHg

fluids:  crystalloids\_\_\_\_\_ml  colloids\_\_\_\_\_ml  
 blood\_\_\_\_\_ml

blood loss\_\_\_\_\_ml end\_surgery Hb\_\_\_\_\_ end\_surgery lactate\_\_\_\_\_

use of vasopressors  max dose\_\_\_\_\_

use of inotropes  max dose\_\_\_\_\_

arrhythmia during surgery  use of antiarrhythmics

Diuresis: total \_\_\_\_\_ml  use of diuretics: \_\_\_\_\_ dose\_\_\_\_\_

End-surgery medication:  NSAIDs

Extubation at the end of surgery  PACU  ICU

**POSTOP :**

	6h	12h	24h	48h	72h	4d	5d	6d	7d	ICU discharge	H discharge	30d	1y
sCr													
eGFR													
urea													
Troponin													
BNP													
Hb													
NGAL													
diuresis													
Fluids in													
drainages													
diuretics													
vasopressors													
inotropes													

\*NA if not present in the medical records

**Outcomes:**

need for RRT: \_\_\_\_\_days

MACCE within 30 days:  AMI

congestive heart failure

non-fatal cardiac arrest

new cardiac arrhythmia

angina

stroke

pulmonary complications within 30 days:  respiratory infection at \_\_\_\_day (i.e. patients has received antibiotics for a suspected respiratory infection + one of the following: new or changed sputum, new or changed opacities, fever, wbc >12000)

respiratory failure at \_\_\_\_day (PaO2 < 60 mmHg at room air, a P/F < 300 mmHg or SpO2 <90% requiring oxygen therapy)

pleural effusion at \_\_\_\_day

atelectasis at \_\_\_\_day

pneumothorax at \_\_\_\_day

bronchospasm at \_\_\_\_day (bronchodilators treatment for new expiratory wheezing)

aspiration pneumonitis at \_\_\_\_day

length of CMV \_\_\_\_h

need for NIV in \_\_\_\_\_h

surgical complications within 30 days:  fistula       hemorrhage       abscess

**Clavien-Dingo grading of complications:**

I: any deviation from the normal postoperative course without the need for pharmacological treatment or surgical, endoscopic, or radiological interventions. Permitted therapeutic interventions include: drugs such anti-emetics, antipyretics, analgesics, diuretics, electrolytes and physiotherapy. Also included wound infections opened at the bedside

- II: drugs other than grade I
- III: requiring surgical, endoscopic, or radiological interventions
  - IIIa: not under general anesthesia
  - IIIb: under general anesthesia
- IV: life-threatening complication (including CNS complications) requiring critical care
  - IVa: single-organ dysfunction (including KRT)
  - IV b: multi-organ dysfunction
- V: death of a patient

Day of ICU discharge: \_\_\_\_\_

Alive

Dead

Day of H discharge: \_\_\_\_\_

Alive

Dead

Death at 30 days after surgery

readmission \_\_\_\_\_ (date)

second surgery

